8.3 ADVERSE EVENTS AND SERIOUS ADVERSE EVENTS

8.3.1 ADVERSE EVENTS

Any event due to the presence or progression of illness that a patient had on study enrollment will not be considered an adverse event (AE), including changes in symptoms, hospitalizations, emergency department presentations, and death more likely related to disease progression than not related to disease progression. Only events more likely not related to known underlying illness will be considered an AE.

If such an event is also related to the research and is unanticipated, regardless of its level of severity, this would require expedited (prompt) reporting to the local IRB in keeping with its reporting requirements for a suspected unanticipated problem involving risks to subjects or others (suspected UPIRTSO).

AEs are classified as to whether or not they are serious (SAE), namely life threatening (resulting in hospitalization, emergency department presentation or death), leading to permanent disability or judged a SAE by the site PI. AEs will be graded according to seriousness, and then designated as more likely expected or unexpected (yes/no), and more likely related or unrelated to the research (yes/no). Other characteristics of the AE to be recorded include date identified, diagnosis, outcome and date resolved.

SAEs will be classified as to whether or not they are a Suspected Unexpected Serious Adverse Reaction. (SUSAR) SUSARs are defined as events that are a suspected adverse reaction AND serious AND unexpected. This approach focuses the Safety Officer's and IRB's attention on potentially study participating-related events rather than on a large number of anticipated events that are part of normal disease progression and unrelated to the intervention. If a SUSAR, then expedited reporting and processes must be followed, as outlined below. If not a SUSAR, standard reporting for AEs is followed (for all AEs and SAEs), unless, as described above, the event meets the definition of a suspected Unanticipated Problems Involving Risks to Subjects or Others (UPIRTSO). An event can be a SAE, but not a SUSAR (e.g. a person hospitalized for hip fracture and not attributable to underlying known illness, but not suspected to be related to the study intervention).

The ECC will review a pre-specified proportion of all hospitalizations and deaths. The ECC will determine if the hospitalization/death or drug related problem (DRP) was an expected event, SAE, or SUSAR. Results will be reported to the Safety Officer and the NIA Project Officer.

Cumulative aggregated AE data will be presented to the Safety Officer and the NIA Project Officer, along with tabulated outcomes data. This includes AEs, SAEs and SUSARs, plus survival, health resource utilization, and patient reported outcomes.

The Study PI is also responsible for contacting the NIH grant program officer in the event that any action resulting in temporary or permanent suspension of the trial occurs. (Because this trial does not involve any investigational medication, the action would be limited to an IRB- or investigator-initiated suspension or discontinuation of the study.)

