3 OBJECTIVES AND ENDPOINTS

| OBJECTIVES | ENDPOINTS | JUSTIFICATION FOR ENDPOINTS | PUTATIVE MECHANISMS OF ACTION |
|-------------------------------|---|---|-------------------------------------|
| Primary | | | |
| Feasibility and Acceptability | 
 • Intervention Delivery to Hospice Staff • Patient and Family Caregiver Recruitment Goals • Completion of FCGs Assessments • Completion of Patient Assessments • Time for completing FCG assessments • Time for completing Patient Assessments • Yield of FCG Eligibility Criteria • Yield of Patient Eligibility Criteria | 
 • Measurements of Intervention Uptake • Measures of Recruitment Yield • Measure of Outcome Assessment Success | |
| Secondary | | | |
| Efficacy and Safety | 
 • FCG Burden • Medication Regimen Complexity • Patient-Centered Medication Communication | 
 • Primary Outcome for trial • Patient medication burden • Quality of prescribing for patients | |

| OBJECTIVES | ENDPOINTS | JUSTIFICATION FOR ENDPOINTS | PUTATIVE MECHANISMS OF ACTION |
|-----------------------------|--|--|-------------------------------------|
| | 
 Potentially Inappropriate Medications, as measured by modified Medication Appropriateness Index Medication changes Patient QOL, as measured by McGill QOL Questionnaire Patient Symptoms, as measured by Edmonton Symptom Assessment System (ESAS) Overall Survival Suspected Unexpected Serious Adverse Reactions (SUSAR) Drug Related Problems | 
 Key patient outcome Key patient outcome Key patient outcome Assessment of risk for study population Risk assessment for intervention | |
| Tertiary/Exploratory | | | |
| | | | |

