6.3 MEASURES TO MINIMIZE BIAS: RANDOMIZATION AND BLINDING

Randomization is at the level of the office location within each hospice agency.

Outcomes assessments will be blinded with withholding intervention assignment data from the clinical research coordinator responsible for data collection related to the measurement of patient and family-caregiver outcomes and from the adjudication team responsible for measuring ADE and ADWEs.

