9.4.7 SUB-GROUP ANALYSES

Analyses by intervention and control status.

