10.1.6 SAFETY OVERSIGHT

Safety oversight will be under the direction of a Safety Officer (SO) who is a physician with relevant study and disease-specific expertise appointed by the study sponsor/NIA. The SO is independent from the study conduct and free of conflict of interest, or measures should be in place to minimize perceived conflict of interest. The SO will review the safety and data monitoring plan, informed consent documents, and participant recruitment and retention milestones. At predetermined intervals (e.g. every 3 months) the study team will prepare safety reports to be reviewed by the SO and the NIA for recommendations for or against the trial's continuation, as well as any modification to the study. The SO will be unblinded to safety data.

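### SUSAR status turns on suspected relation to a programme that only one arm receives, so a by-arm SUSAR count is not a valid comparison of harm

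*Combined protocol and SAP*

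**What the plan says.** All references are to the combined protocol and SAP.

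- **Endpoint.** Section 3 (Objectives and Endpoints) lists "Suspected Unexpected Serious Adverse Reactions (SUSAR") among the secondary efficacy and safety endpoints. Drug-related problems (DRPs) are listed beside it.
- **By-arm analysis.** Section 9.4.7 consists of one line: "Analyses by intervention and control status". It names no endpoint.
- **Definition.** Section 8.3.1 states that "SUSARs are defined as events that are a suspected adverse reaction AND serious AND unexpected". This sentence does not say what the reaction is a reaction to.
- **Referent.** The only worked example in Section 8.3.1, a hip fracture, is an SAE but not a SUSAR because it is not due to known illness "but not suspected to be related to the study intervention". The same section rates every AE as "more likely related or unrelated to the research (yes/no") and describes SUSARs as a way to focus attention on events linked to taking part in the study.
- **Classifier.** Section 8.3.1 states: "The ECC will determine if the hospitalization/death or drug related problem (DRP) was an expected event, SAE, or SUSAR". Section 8.2 gives the monitoring of relation to the research to an Event Classification Pharmacist (ECP).
- **Blinding.** Section 6.3 withholds assignment from the coordinator who collects outcomes and "from the adjudication team responsible for measuring ADE and ADWEs". Section 10.1.6 says of the Safety Officer: "The SO will be unblinded to safety data".
- **Exposure.** Under Section 6.1.1 only staff in intervention offices are given SPECTORx during the trial. Control staff are referred to a public website, and control participants receive a study notebook.

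**The concern.** A harm endpoint compared between arms needs one rule that can be applied in the same way to both. SUSAR status requires a judgement that the event is suspected to be related to something. If that something is SPECTORx, control patients were never exposed to it.

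Take the same serious withdrawal event after the same drug was stopped, once in each arm. In the intervention office the stop may be traced to the programme. In the control office it is ordinary care. The clinical harm is identical, but only one event can be counted.

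Adverse drug withdrawal is the risk that the protocol itself names for deprescribing (Section 2.3.1), and the pilot is meant to inform a larger trial (Section 9.4.3). A count built on this attribution could suggest an excess on SPECTORx where none exists. It could not show serious drug harm that the programme prevented.

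**Working it through.** **Plan's own figure.** The plan gives no SUSAR rate, test, alpha or margin, so there is no SUSAR figure to reproduce. The enrolment target follows from Section 4.1: 2 agencies × 2 offices × 15 dyads = 60, or 30 per arm. It matches.

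**Step 1: the possible readings.** The text leaves two things open: the referent of suspected relation, and whether the classifier knows the arm.

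| Relation is to | Classifier knows the arm | Classifier is blind |
|---|---|---|
| SPECTORx | Control events cannot qualify; the rule differs by arm | Can judge whether a drug or a drug stop caused the event, not whether SPECTORx caused the stop |
| The research or participation | Control events can qualify, but the study exposure being judged differs by arm | Same rule in both arms, but what is rated is in effect drug causation, not relation to the intervention |

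Only the last cell gives a symmetric rule. What it counts is a serious, unexpected drug-related event, which should then be defined and named as such. No cell gives a SUSAR count that is both symmetric and a measure of relation to SPECTORx.

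**Step 2: which cell applies.** The documents do not say. Section 6.3 blinds the team that measures ADEs and ADWEs. Section 8.3.1 has the ECC classify SUSARs, and Section 8.2 names the ECP. Neither is said to be blinded, and neither is said to be the Section 6.3 team.

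**Step 3: illustration only.** Every rate here is assumed. Let s be the risk of an unexpected serious event (5% to 30%, equal in both arms) and q the chance that it is judged suspected (10% to 50%). Clustering is ignored.

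- Expected SUSARs per exposed arm = 30 × s × q. Lowest: 30 × 0.05 × 0.10 = 0.15. Highest: 30 × 0.30 × 0.50 = 4.5.
- P(at least one) = 1 − (1 − sq)^30. Lowest: 1 − 0.995^30 = 0.14. Highest: 1 − 0.85^30 = 0.99.
- With a blind classifier these values apply to both arms, so the control count is not forced to zero.
- With an arm-aware classifier and relation meaning SPECTORx, they apply to the intervention arm only and control is 0. Any difference is then spurious.
- If a test were run with control fixed at 0/30, Fisher's exact p is 0.052 for 5/30 and 0.024 for 6/30. The chance of 6 or more in the intervention arm with no true effect runs from below 0.001 to 0.29.

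The width of these ranges shows that the documents cannot support a single estimate of the distortion.

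**The case against.** A reader might infer that control SUSARs are zero by construction. The text does not go that far. The defining sentence names no referent, the AE rating is relation to the research, and control participants do have study exposure through the notebook and the material chosen by the study. Zero follows only if relation means SPECTORx and the classifier knows the arm.

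A reader might also infer that the plan requires a blinded body to judge relation to SPECTORx. That needs the ECC or ECP to be the blinded team of Section 6.3, and no section says so. The two inferences also pull against each other, because a blinded classifier can call control events suspected.

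Other points stand as well:

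- Measures that need no relation to the study already exist. The synopsis (Section 1.1) lists time to first hospital or emergency admission whether or not study-related, and adverse drug withdrawal events. Section 3 lists DRPs. Section 8.3.1 keeps unrelated SAEs and reports them. Serious drug harm avoided by deprescribing can therefore appear elsewhere in the results.
- No SUSAR test is planned, interim endpoint summaries are descriptive by default (Section 9.4.6), and Section 9.2 disclaims power for efficacy.
- Because Section 2.3.1 names withdrawal events as a known risk, some could be rated expected and fail the SUSAR definition in either arm.

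What the objection does not remove is that Section 3 lists SUSAR as an endpoint, its referent shifts within Section 8.3.1, and its classifier's blinding is unstated. Nor does Section 9.4.4 name any between-arm harm comparison that is free of attribution.

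**Conclusion.** The point holds in a limited form. As written, a by-arm SUSAR count does not validly compare harm: an arm-aware classifier who takes relation to mean SPECTORx applies a rule that control events cannot meet, and a blind classifier cannot judge relation to SPECTORx. The effect is on how one secondary safety endpoint can be interpreted. It does not touch the feasibility endpoints, and it does not leave the trial without harm data.

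The size cannot be estimated from the documents. The ranges in the illustration rest wholly on assumed event risks and attribution fractions, and a zero control count is one reading of the text rather than a consequence of it. This is a cheap improvement worth making before the safety endpoints are tabulated by arm.

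**What to change.** **Sections 3 and 9.4.4.** Base the between-arm harm comparison on the number of patients with a serious drug-related event (ADE, ADWE or DRP) and on all SAEs, regardless of attribution to the research and classified blind to arm. Keep SUSAR for expedited reporting and list it descriptively only.

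**Section 8.3.** Use one referent for a suspected reaction throughout. State how the ECC and the ECP relate to each other and to the team in Section 6.3, and whether they are blinded. Make any judgement of relation to SPECTORx a separate step, taken after the blinded classification is recorded. The plan may choose who takes that step. Moving it to the unblinded Safety Officer is not needed, and would turn an oversight role into event-level adjudication.

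**Cost.** Wording in these sections, plus slightly more classification and tabulation. Section 8.3.1 has the ECC review only a pre-specified proportion of hospitalizations and deaths, so a comparison on all SAEs needs the full set classified. With 60 patients that means at most 60 deaths, plus hospitalizations, which Section 8.2 expects to be unusual. The underlying drug-event, SAE and utilization data are already to be collected.

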8.2 SAFETY ASSESSMENTS

In accordance with applicable regulatory requirements and principles for the ethical conduct of research, a Safety Officer will be appointed by the NIA to oversee the safety of study participants.

Because the study population has, per the eligibility criteria, a limited expected prognosis of less than one year, death and the preceding associated development of symptoms related to the natural progression of disease are expected. Because the study setting is home hospice, hospitalizations related to the natural progression of disease are expected to be unusual. However, deaths, hospitalizations, and emergency department visits will be monitored.

Because the focus of the trial educational intervention focuses on medication-related management, review and support, medication changes and symptom changes potentially related to drug related problems (DRPs) will be monitored, including potential DRPs present upon study enrollment which, by definition, are not related to the research.

Medication changes will be identified by collecting medication lists every 2 weeks and iteratively identifying changes between lists. DRPs will be monitored by a trained research assistant who will screen the medical record using a Screening Algorithm of Potential Drug Related Problems at *study enrollment and every 2 weeks up to 2 months* for a retrospective chart review, and then monthly up to 6 months. These medical record will be reviewed for new clinical events, symptoms, abnormal lab events and drug levels, new reported drug allergies or drug associated problems identified by clinicians. Secondarily, a trained research assistant will also conduct a screening telephone interview with patients (or their caregiver, if patient is unable to participate) for potential DRPs using a method by Chrischilles³¹ *at 2 weeks and monthly* thereafter.

To ensure that potential DRPs, emergency department visits, hospitalizations and deaths are indeed unrelated to the research, these will be closely monitored by the study's Event Classification Pharmacist (ECP) comprised of a pharmacist using a procedure described below in Section 8.3.

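### Section 8.2 promises that ED visits, hospitalizations, deaths and drug-related problems are all checked for relatedness, but the section 8.3 procedure samples an unstated share of hospitalizations and deaths and does not name ED visits

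*Combined protocol and SAP*

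**What the plan says.** Section 8.2 sets the aim: "To ensure that potential DRPs, emergency department visits, hospitalizations and deaths are indeed unrelated to the research, these will be closely monitored". The work goes to the "Event Classification Pharmacist (ECP) comprised of a pharmacist using a procedure described below in Section 8.3". Four event types are named and no sampling is mentioned. The same section also states that "deaths, hospitalizations, and emergency department visits will be monitored".

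Section 8.3.1 then describes the review: "The ECC will review a pre-specified proportion of all hospitalizations and deaths". The next sentence says what the review decides: "The ECC will determine if the hospitalization/death or drug related problem (DRP) was an expected event, SAE, or SUSAR". Neither sentence mentions ED visits. No value for the proportion, and no rule for choosing events, appears in the supplied text. The ECC is not defined there and is not in the abbreviations list (section 10.3).

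Three other parts of the plan bear on the point.

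- Section 8.3.1 excludes from adverse events (AEs) anything judged more likely to come from illness present at enrollment, including hospitalizations, ED presentations and deaths. What remains is graded for seriousness, expectedness and relatedness. The definition of a serious AE (SAE) covers events that are "life threatening (resulting in hospitalization, emergency department presentation or death".
- Section 8.2 has a research assistant screen charts for potential DRPs at enrollment, two-weekly for 2 months and then monthly to 6 months. Telephone screening is added at 2 weeks and monthly after that.
- Section 6.3 refers to a blinded adjudication team for adverse drug events and adverse drug withdrawal events. Section 10.2, headed as the place where these are determined, has no content in the supplied text.

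**The concern.** An assurance about all events of four types cannot rest on a review of an unstated share of two of them, with DRPs added and ED visits left out. The two sections also name different reviewers, and section 6.3 adds a third name.

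This matters because the intervention trains staff to stop or taper medications, and section 2.3.1 names adverse drug withdrawal events as a risk. Suspected unexpected serious adverse reactions (SUSARs) and DRPs are listed as secondary endpoints in section 3. The Safety Officer's reports contain AE, SAE and SUSAR tabulations. In hospice, disease progression is the natural explanation for almost any deterioration, so a drug-related event is easily put down to it. An independent check on that attribution is where the safety review adds most.

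**Working it through.** **1. The two sections side by side**

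| Item | Section 8.2 | Section 8.3.1 (ECC sentences) |
|---|---|---|
| Reviewer | Event Classification Pharmacist (ECP) | ECC, not defined |
| DRPs | included | included, no sampling stated |
| Hospitalizations, deaths | included, no sampling stated | a proportion, no value given |
| ED visits | included | not named |
| How events are selected | not applicable | not stated |

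**2. Tracing an event through the plan**

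Take a hospitalization or death that is in truth drug-related.

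- If it is accepted as an AE, it is graded for relatedness, with no sampling.
- If chart or telephone screening flags it as a DRP, it can reach the ECC, again with no sampling.
- If it is attributed to disease progression, it is not an AE, so the grading never starts. Section 8.3.1 does not name who makes that judgement. If it is also not flagged as a DRP, the only remaining check is the ECC's proportion. Outside that proportion there is none.

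For an ED visit that does not lead to admission, the third path has no ECC check at all, whatever the proportion.

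**3. Illustration of the sampling effect**

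The plan states no figure here, so there is none to reproduce. Two quantities must be assumed: the fraction reviewed, f, and the number of drug-related hospitalizations or deaths, k. Selection is assumed random, which the plan does not say.

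- P(at least one of k not reviewed by the ECC) = 1 − f^k
- P(none of k reviewed by the ECC) = (1 − f)^k

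For k = 3 and f = 0.50: 1 − 0.50³ = 0.875 and (1 − 0.50)³ = 0.125.

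| f | k = 1: not reviewed | k = 3: at least one not reviewed | k = 3: none reviewed |
|---|---|---|---|
| 0.25 | 75% | 98.4% | 42.2% |
| 0.50 | 50% | 87.5% | 12.5% |
| 0.75 | 25% | 57.8% | 1.6% |
| 0.90 | 10% | 27.1% | 0.1% |
| 1.00 | 0% | 0% | 0% |

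These are chances of falling outside the ECC's review. They are not chances of going undetected by every route.

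**4. Size of a full review**

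Enrollment is 2 agencies × 2 offices × 15 dyads = 60, which matches the stated total, so there can be at most 60 deaths. Section 8.2 expects hospitalizations from natural progression to be unusual. It gives no expected number of ED visits or DRPs.

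**The case against.** The strongest reply is that the ECC review is a second look and not the only route. Section 8.3.1 grades all AEs and classifies all SAEs without sampling, and gives the site investigator a part in judging seriousness. The DRP part of the ECC's task is not sampled either, and DRP screening is frequent and covers new clinical events. A reader might infer that an event outside the sample is never classified. The documents do not support that: at most, the ECC does not classify it. The gap is confined to events attributed to progression and not flagged as DRPs.

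A reader might also infer that section 8.3 ignores ED visits. It does not; they appear in its AE rule and its SAE definition. Only the two ECC sentences leave them out.

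The word pre-specified suggests that the proportion is recorded somewhere, perhaps in the Manual of Procedures, which was not supplied. It could be 100%. In that case the sampling part of the concern disappears and stating the figure costs nothing, but the ED omission and the mismatch of reviewers remain.

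Finally, one could say that full review is trivial work because these events are rare. Section 8.2 says so only of progression-related hospitalizations, so the workload from ED visits and DRPs is unknown.

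**Conclusion.** Sections 8.2 and 8.3 are inconsistent on who reviews, which events are reviewed and what share of them. As written, the 8.3 procedure cannot deliver the 8.2 assurance. A hospitalization or death attributed to progression, not flagged as a DRP and outside the sample gets no independent classification. An ED visit attributed in this way gets none at any fraction.

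The size cannot be computed from the plan. Under random sampling with 3 drug-related hospitalizations or deaths, the chance that the ECC does not review at least one runs from 98% at 25% review to 0% at full review. The fraction, the number of events and the random selection are all assumptions.

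It would go too far to say that SAEs and SUSARs will be undercounted; they may be, if the unsampled routes also fail. The secondary outcome of time to first hospital or ED admission counts admissions for any reason, so it does not depend on this classification. Nor does the feasibility primary endpoint. The point concerns safety oversight and the SUSAR endpoint, and deserves a correction because the remedy is cheap.

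**What to change.** Replace the sampling sentence in section 8.3.1 with: *The ECP will review and classify all hospitalizations, emergency department visits, deaths and screened-positive DRPs.* Add ED visits to the classification sentence that follows, and use one name for the reviewing body in sections 8.2 and 8.3.

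State whether this reviewer is the blinded adjudication team of section 6.3. Nothing in the plan says that it is, so blinding of the ECP should not be taken as given. It would also help to say who first decides between AE and disease progression.

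If the sponsor prefers to keep a proportion, the protocol should give its value and the selection rule, and section 8.2 should promise only what that proportion can support.

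The cost is additional reviewer hours. The reviewer is already named, and the schedule of activities already collects survival, hospital admissions, ED visits and DRP screens, so no new data are needed. Hours for deaths are bounded by 60 patients. Those for ED visits and DRPs cannot be estimated from the plan and should be checked before the sponsor commits to full review.
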